- ^e Vital sign measurements will be collected after the participant has been at rest for a least 5 min. Vital signs will include sitting blood pressure, heart rate, respiratory rate, and temperature. Weight will be collected at all study visits.
- ^f Single 12-lead ECGs will be obtained locally after the participant has been at rest for a least 5 min. ECGs will be performed only if clinically indicated after C13D1.
- ^g For all visits, a -3-day window is allowed for laboratory assessments. Local laboratory results may be used for treatment management decisions during the study. Safety samples should be drawn predose at each visit.
- ^h Surgical assessment questionnaire should be completed prior to surgery for participants who proceed to surgery during the study, to capture post-treatment status.
- ⁱ On all planned PK sampling days, the participant will be dosed in the clinic. On all other visits, participants may dose at home.
- ^j A single PK sample will be collected predose (within 60 min before dosing) on Day 1 at C7, C10, and C13 (Week 49) or EOT, whichever occurs first. On PK sampling days, the order of events should be ECG, vital signs, and then PK sample collection. An unscheduled PK sample may be taken at the time of the onset of a new suspected, treatment-related AE as deemed medically appropriate by the Investigator and Sponsor.
- ^k Pharmacodynamic samples (whole blood and plasma) will be collected predose on C7D1, C10D1, and C13D1 or EOT, whichever occurs first. Asia and Pacific countries only: whole blood sample will not be collected.
- ¹ An MRI of the affected joint will be performed every third cycle after End of Part 1 visit starting on C10D1 (±7 days), Day 1 (±7 days) of every 3 cycles thereafter, at the EOT visit (if not performed within the previous 30 days), and 12 weeks (±4 weeks) after last dose of study drug at the first Disease Follow-up Visit.
- ^m ROM assessment (active and passive) of the affected joint only will be assessed as of C10D1 and every 3 cycles (ie, C13D1 [\pm 7 days], C16D1 [\pm 7 days], etc.), and at the EOT visit (if not performed within the previous 30 days). Assessments should ideally be performed by the same person for consistency.
- ⁿ CGIC, CGIC (ROM), CGIC (PF), CGIS (ROM), and CGIS (PF) will be collected during clinic visits until C25 or EOT.
- ^o PRO questionnaires will be delivered on an electronic device per schedule described in Table 5.
- ^p Participant will complete a dosing diary daily between site visits. Site Staff must review the dosing diary at each clinic visit and collect all completed dosing diaries from the participant.
- ^q Narcotic analgesic medication use will be recorded by participant diary through C12 (Week 48) or until EOT, whichever occurs first. Site staff must review this diary at each clinic visit and collect all completed narcotic analgesic diaries from the participant.
- ^r For additional information refer to Section 11.9.12.

Screening ^a							
Day of Week	Day 1	Day 2	Day 3	Day 4	Day 5	Day 6	Day 7
Week 1	BPI NRS	BPI NRS	BPI NRS	BPI NRS	BPI NRS	BPI NRS	BPI NRS PROMIS ^b
							EQ-5D-5L ^b
							PGIS (PF) ^b
			_				PGIS (ROM) ^b
Week 2	BPI NRS	BPI NRS	BPI NRS	BPI NRS	BPI NRS	BPI NRS	BPI NRS
Cycle 1				l			
Day of Week	Day 1	Day 2	Day 3	Day 4	Day 5	Day 6	Day 7
Week 1		BPI NRS GP5 ^c	BPI	BPI NRS	BPI	BPI NRS	ВЫ
Week 2	BPI NRS	BPI	BPI NRS GP5 ^c	BPI	BPI NRS	BPI	
Week 3	BPI NRS GP5 ^c PROMIS ^c EQ-5D-5L ^c PGIC ^c PGIS (PF) ^c PGIC (PF) ^c PGIS (ROM) ^c PGIC (ROM) ^c		BPI	BPI NRS	BPI	BPI NRS	BPI
Week 4							

Table 4: Schedule of Patient-reported Outcome Assessments in Part 1

Cycles 2 through 6							
Day of Week	Day 1	Day 2	Day 3	Day 4	Day 5	Day 6	Day 7
Week 1	BPI NRS GP5 ^c PROMIS ^c EQ-5D-5L ^c PGIC ^c PGIS (PF) ^c PGIC (PF) ^c PGIS (ROM) ^c PGIC (ROM) ^c	BPI	BPI NRS	BPI	BPI NRS	BPI	BPI NRS GP5
Week 2	BPI	BPI NRS	BPI	BPI NRS	BPI	BPI NRS PROMIS ^c GP5 ^c PGIS (PF) ^c PGIC (PF) ^c	BPI
Week 3	BPI NRS	BPI	BPI NRS	BPI	BPI NRS GP5 ^c	BPI	BPI NRS
Week 4							
End of Part 1	•	-	-			•	•
At End of Part 1 Visit (Blinded, see Table 12)	BPI NRS GP5 ^c PROMIS ^c EQ-5D-5L ^c PGIC ^c PGIS (PF) ^c PGIS (PF) ^c PGIS (ROM) ^c PGIC (ROM) ^c						

EOT Visit ^d											
Within 7 days of decision to stop drug	BPI NRS GP5 PROMIS EQ-5D-5L PGIC PGIS (PF) PGIC (PF) PGIS (ROM) PGIC (ROM)										

Abbreviations: BPI=Brief Pain Inventory; EOT=End-of-Treatment; EQ-5D-5L=5-level EQ-5D; FACT-G=Functional Assessment of Cancer Therapy-General; GP5="burden-of-side-effects" question from the FACT-G; NRS=numeric rating scale on stiffness; PF=Physical Function; PGIC=patient global impression of change; PGIS=patient global impression of severity; PROMIS=Patient-reported Outcomes Measurement Information System; ROM=range of motion.

^a Over any 14 consecutive day period during screening, participant must complete at least 4 baseline assessments for BPI (Worst Pain question only) and Worst Stiffness NRS items; and at least one baseline PROMIS assessment, and one baseline EQ-5D-5L assessment to meet entry criteria.

^b A +7-day window is allowed for completing the PROMIS, PGIS (PF), PGIS (ROM), and EQ-5D-5L questionnaires during screening only.

^c The GP5, PROMIS, EQ-5D-5L, PGIC, and PGIS questionnaires are allowed a +2-day window during treatment cycles.

^d No window is allowed at the EOT visit.

Table 5: Schedule of Patient-reported Outcome Assessments in Part 2

Cycles 1 Crossove	r (crossover participan	ts)					
or							
Cycles 7 (participa	ants continuing vimselti	nib)					
Day of Week	Day 1	Day 2	Day 3	Day 4	Day 5	Day 6	Day 7
Week 1		BPI NRS GP5	BPI	BPI NRS	BPI	BPI NRS	BPI
Week 2	BPI NRS	BPI	BPI NRS GP5	BPI	BPI NRS	BPI	
Week 3	BPI NRS GP5 PROMIS EQ-5D-5L PGIC PGIS (PF) PGIC (PF) PGIS (ROM) PGIC (ROM)		BPI	BPI NRS	BPI	BPI NRS	BPI
Week 4							

Cycles 2 through 6	6 (crossover participan	ts)					
or							
Cycles 8 through 1	12 (participants continu	ung vimseltinib)					
Day of Week	Day 1	Day 2	Day 3	Day 4	Day 5	Day 6	Day 7
Week 1	BPI NRS GP5 PROMIS EQ-5D-5L PGIC PGIS (PF) PGIC (PF) PGIS (ROM) PGIC (ROM)	BPI	BPI NRS	BPI	BPI NRS	BPI	BPI NRS GP5
Week 2	BPI	BPI NRS	BPI	BPI NRS	ВЫ	BPI NRS PROMIS GP5 PGIS (PF) PGIC (PF)	BPI
Week 3	BPI NRS	BPI	BPI NRS	BPI	BPI NRS GP5	BPI	BPI NRS
Week 4							

Cycles 7 through 18 (crossover participa	nts)					
or		-					
Cycles 13 through 24	(participants contin	uing vimseltinik))				
Day of Week	Day 1	Day 2	Day 3	Day 4	Day 5	Day 6	Day 7
Week 1	BPI NRS GP5 PROMIS EQ-5D-5L PGIC PGIS (PF) PGIC (PF) PGIS (ROM) PGIC (ROM)						
Week 2							
Week 3							
Week 4							
EOT visit				I			
Within 7 days of decision to stop drug	BPI NRS GP5 PROMIS EQ-5D-5L PGIC PGIS (PF) PGIC (PF) PGIS (ROM) PGIC (ROM)						

Abbreviations: BPI=Brief Pain Inventory; EOT=End-of-Treatment; EQ-5D-5L=5-level EQ-5D; FACT-G=Functional Assessment of Cancer Therapy-General; GP5="burden-of-side-effects" question from the FACT-G; NRS=numeric rating scale on stiffness; PF=Physical Function; PGIC=patient global impression of change; PGIS=patient global impression of severity; PROMIS=Patient-reported Outcomes Measurement Information System; ROM=range of motion. Note: The GP5, PROMIS, EQ-5D-5L, PGIC and PGIS questionnaires are allowed a +2-day window during treatment cycles until EOT; no window is allowed at the EOT visit.

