- Initiation of any other anti-tumor therapy for TGCT, including radiation or surgery
- Investigational therapy or investigational procedures of any kind
- The use of intra-articular steroid injections for treatment of TGCT; use of intra-articular steroids for a non-TGCT condition is permitted
- Acetaminophen usage exceeding 3 g/day
- Proton-pump inhibitors: discontinue at least 4 days prior to the first dose of study drug
- Medications that are BCRP or OCT2 substrates: discontinue at least 4 days or 5×half-life (whichever is longer) prior to the first dose of study drug
- Medications with a known risk of prolonging the QT interval: discontinue at least 14 days or 5×half-life (whichever is longer) prior to the first dose of study drug (Appendix 1)
- Prophylactic use of myeloid growth factors (eg, G-CSF, GM-CSF)

Statistical Methods: Objective response rate will be compared between the 2 treatment arms using a two-sided Cochran-Mantel-Haenszel test stratified by the randomization stratification factors. The test will be performed at a 0.05 alpha level on the intent-to-treat (ITT) set, which includes all randomized participants. A 95% confidence interval (CI) for the proportion in each arm and for the difference in proportion will be presented. Mean change from baseline in ROM, PROMIS-Physical Function score, Worst Stiffness NRS score, and EQ-VAS at Week 25 will be compared between the treatment arms using a mixed model for repeated measurements.

To control overall type I error, a hierarchical testing procedure will be utilized. Statistical testing will be performed for the analysis of primary and key secondary endpoints in the following order at a 2-sided 0.05 alpha level for each:

- 1. ORR per RECIST v1.1 at Week 25
- 2. ORR per TVS at Week 25
- 3. Mean change from baseline in active ROM at Week 25
- 4. Mean change from baseline in the PROMIS-Physical Function score at Week 25
- 5. Mean change from baseline in the Worst Stiffness NRS score at Week 25
- 6. Mean change from baseline in EQ-VAS at Week 25
- 7. Proportion of responders based on BPI-30 (Worst Pain) NRS score and narcotic analgesic use at Week 25

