12.4.5.2. Secondary Efficacy Analyses

As specified in following the sub-sections, multiple secondary endpoints will be analyzed using a mixed model for repeated measurements (MMRM). The dependent variable will be the change from baseline. Each of these models will include fixed effects for treatment group, timepoint, stratification factor for region (U.S. versus non-U.S.), stratification factor for tumor location, and the baseline value of the corresponding endpoint. For the analysis of ROM only, tumor location will be replaced with joint type (knee, ankle, or other). An unstructured variance-covariance matrix will be used. Statistical comparisons between treatment groups will be made at the specified timepoint.

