1. INTRODUCTION

This statistical analysis plan (SAP) contains definitions of analysis populations and endpoints, and provides a comprehensive description of statistical analyses to be implemented to assess the clinical efficacy, safety and tolerability of vimseltinib in the Phase 3, Randomized, Placebocontrolled, Double-blind Study of Vimseltinib to Assess the Efficacy and Safety in Patients with Tenosynovial Giant Cell Tumor (MOTION) (Protocol DCC-3014-03-001 Amendment 3, dated 31 May 2023).

If there are any differences between the protocol's statistical analysis section and the present document, this SAP will be the primary reference for the study's statistical analyses. Any differences will be highlighted in Section 11.

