9.10.3. Key Secondary Endpoints

As specified in the following sub-sections, multiple secondary endpoints will be analyzed using a mixed model for repeated measurements (MMRM) using the sandwich estimator to estimate the variance-covariance matrix. The dependent variable will be the change from baseline. Each of these models will include fixed effects for treatment group, timepoint, treatment group by timepoint interaction, stratification factor for region (U.S. versus non-U.S.), stratification factor for tumor location (lower limb vs. all other), and the baseline value of the corresponding endpoint. Statistical comparisons between treatment groups will be made at the specified timepoint. For the analysis of ROM only, tumor location will be replaced with joint type (knee, ankle, or other). An unstructured variance-covariance matrix will be used. If the unstructured variance-covariance matrix fails to converge, then alternative structures will be utilized. Statistical comparisons between treatment groups will be made based on a contrast statement at Week 25.

Analyses of the secondary endpoints described in the following sub-sections will be limited to data from Part 1 and will focus on comparisons between participants who received vimseltinib versus participants who received placebo during this period. The exception to this rule is for duration of response presented in Section 9.10.4.3.

These analyses may also be performed on the PP Set if the proportion of participants from the ITT Set who are excluded from PP Set exceeds 5%.

A separate analysis plan will describe the process for identifying the minimally clinical important difference (MCID) for PROMIS-PF, Worst Stiffness, and ROM. A responder analysis for each of these endpoints based on the MCID of each endpoint as determined by the analysis will be performed.

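### The four MMRM key secondary tests fit one baseline slope for all visits; adding a baseline-by-timepoint term is a small, conditional gain in Week 25 precision, not a repair of an invalid test

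*Protocol*

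**What the plan says.** The Protocol Synopsis names the method without its terms: mean changes in ROM, PROMIS-PF, Worst Stiffness NRS and "EQ-VAS at Week 25 will be compared between the treatment arms using a mixed model for repeated measurements".

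SAP 9.10.3 specifies one model for the four continuous key secondary endpoints: active ROM, PROMIS-PF, Worst Stiffness NRS and EQ-VAS. "The dependent variable will be the change from baseline". The listed terms begin with "fixed effects for treatment group, timepoint, treatment group by timepoint interaction", continue with region, and end with "stratification factor for tumor location (lower limb vs. all other), and the baseline value of the corresponding endpoint". For ROM, joint type replaces tumor location. The covariance is unstructured, a sandwich estimator is named, and the comparison is a contrast at Week 25.

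The visits are Weeks 13 and 25 for ROM (SAP 9.10.3.2) and Weeks 5, 9, 13, 17, 21 and 25 for the other three (SAP 9.10.3.3 to 9.10.3.5).

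Protocol 12.4.5.2 also has baseline only as a main effect: "stratification factor for tumor location, and the baseline value of the corresponding endpoint". It lists no interaction at all; treatment-by-timepoint appears first in the SAP. The SAP governs, since "this SAP will be the primary reference for the study's statistical analyses" (SAP 1). Neither document lists baseline-by-timepoint.

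**The concern.** The model is flexible everywhere except in the baseline adjustment. Treatment effects and variances are free at each visit, but early visits help to set the slope that adjusts a Week 25 comparison. The correlation of an outcome with its baseline often weakens over time, which makes the slope of change on baseline steeper at later visits. The pooled slope is then too shallow at Week 25, and some baseline variation that could have been removed stays in the residual.

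These endpoints are steps 3 to 6 of the fixed sequence in SAP 9.10.1, where one non-significant result ends formal testing of everything after it. The documents give no effect size, SD or power for any of the four, so they show no reserve of power against which to set a loss.

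**Working it through.** **The plan's own figure.** The only power stated is 98% for the primary endpoint (35% versus 5%, two-sided Fisher's exact test; Protocol 12.1, SAP 5). Exact enumeration gives 98.3% at 80/40 and 96.3% at 68/34, that is, after 15% dropout. The figure reproduces, but it says nothing about the MMRM tests.

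**Formula.** Treatment-by-timepoint is saturated. With complete data, and leaving out the stratification covariates, the Week 25 estimate is D_Y − b·D_X. Here D_Y and D_X are the arm differences in Week 25 change and in baseline, and b is the pooled slope:

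- b = (1′Σ⁻¹β) / (1′Σ⁻¹1), with β the visit slopes and Σ the residual covariance.
- Variance ratio, common slope over visit-specific slopes: r = 1 + σ_X²(β₂₅ − b)² / σ₂₅².
- Power after the loss, for a test planned at power p: Φ((1.96 + z_p)/√r − 1.96).

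**Assumed inputs (none is in the documents).** Baseline SD 1.8; Week 25 residual SD 1.9; AR(1) correlation 0.6 to 0.8; slopes moving linearly from the first model visit to Week 25. Residual SD is either equal at all visits or rises from 1.5 to 1.9.

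**Equal SDs.** The weights are symmetric over visits, so b is the midpoint of the slopes, here −0.35:

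- Mild, −0.3 to −0.4: r = 1 + 3.24 × 0.05²/3.61 = 1.002.
- Moderate, −0.2 to −0.5: r = 1 + 3.24 × 0.15²/3.61 = 1.020.
- Strong, −0.1 to −0.6: r = 1 + 3.24 × 0.25²/3.61 = 1.056.

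**Rising SDs.** Early visits gain weight, so the gap at Week 25 widens. For moderate drift over six visits, b = −0.321 (correlation 0.6) or −0.303 (0.8).

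| Drift | Visits | r, equal SDs | r, rising SDs |
|---|---|---|---|
| None | 6 or 2 | 1.000 | 1.000 |
| Mild | 6 | 1.002 | 1.003-1.004 |
| Mild | 2 (ROM) | 1.002 | 1.005-1.009 |
| Moderate | 6 | 1.020 | 1.029-1.035 |
| Moderate | 2 (ROM) | 1.020 | 1.049-1.085 |
| Strong | 6 | 1.056 | 1.080-1.097 |

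**Power, for a test planned at 80%.** Moderate, six visits: 79.2% falling to 78.7%. Moderate, ROM: 79.2% falling to 76.7%. Strong, six visits: 77.8% falling to 76.3%.

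**Second parameterisation.** Take outcome SD 1 at every visit, between-visit correlation 0.6 to 0.9, and a falling correlation with baseline. The SE ratios, and their squares as variance, are:

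- Six visits, 0.75 to 0.50: SE 1.014-1.021, variance 3-4% larger.
- Six visits, 0.80 to 0.40: SE 1.039-1.069, variance 8-14% larger.
- ROM, 0.80 to 0.60: SE 1.015-1.057, variance 3-12% larger.
- Six visits, 0.80 to 0.20, an extreme case: SE 1.09-1.22.

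The upper ends come from between-visit correlation 0.9.

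**Simulation** (unstructured MMRM, 80/40, 600 runs per scenario, model-based SEs, with and without about 11% missing-at-random dropout). Under strong drift the type I error was 0.045-0.050 with the common slope and 0.047-0.057 with visit-specific slopes. Bias was at most about 0.015 SD and nearly equal in the two models. Power differed by 0.7-1.2 points (moderate) and 2.0-2.6 points (strong). In the strong case with dropout the mean SE was 0.1968 against 0.1877, and power 70.2% against 72.8%. With a constant slope the SEs were the same, 0.1548 in both models in the complete-data null run.

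**The case against.** The strongest reply is that nothing is wrong. A common baseline slope is a legitimate prespecified choice, and the simulation shows no bias or type I inflation. That stands. A reader might infer from the missing term that the Week 25 comparison is biased or its error rate uncontrolled; neither the documents nor the calculations support that.

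The second reply is that the loss needs a drift that the documents never describe. This also stands. Protocol 5.2 says that tumor responses in the earlier study generally came after two or more cycles, but that concerns tumor response, not slopes on baseline. A reader might infer that precision is certainly being thrown away, or turn the ratios into a fixed number of lost participants. Both go too far: with a constant slope the loss is zero. If the slope steepens early and then levels off (−0.2, −0.35, −0.43, −0.47, −0.49, −0.5, equal SDs) it is 1.1-1.4%.

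The size also depends on residual SDs that are not given: moderate drift in the ROM model runs from 2.0% with equal SDs to 8.5% with rising ones.

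Chance baseline imbalance that is only partly removed might look like a second harm. It is the same one: σ_X²(β₂₅ − b)² is that leftover imbalance averaged over randomizations.

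The sandwich estimator answers only part of the point. It protects the standard error under misspecification but does not restore lost precision.

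**Conclusion.** The point holds as a minor, optional improvement in efficiency. All four MMRM tests use one baseline slope while testing only Week 25. The planned test is valid, no figure in the plan is wrong, and no passages conflict on this term.

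The gain from visit-specific slopes is nil if the slope is constant, under 1% of variance for mild drift, 2-4% for moderate drift over six visits, 2-8% for moderate drift in the ROM model, and 6-10% for strong drift over six visits. In power this is roughly 0 to 3 points, with 3.7 at the far corner of the first set of scenarios. More extreme assumptions give more, but nothing in the documents points to them.

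Every slope, SD and correlation here is an assumption. The formula assumes complete data and omits the stratification covariates; the simulation used model-based rather than sandwich SEs. If the slope became shallower by Week 25, the contrast would be over-adjusted instead, and the loss would again follow the squared gap.

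**What to change.** In SAP 9.10.3, add a baseline-by-timepoint interaction to the fixed effects of the MMRM for active ROM, PROMIS-PF, Worst Stiffness NRS and EQ-VAS, next to "and the baseline value of the corresponding endpoint", and state that the Week 25 treatment contrast comes from that model. Record the added term in SAP 11, where SAP 1 says that differences from the protocol are to be highlighted.

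The cost is one phrase and 6 − 1 = 5 parameters for each six-visit model, or 2 − 1 = 1 for ROM. No new data are needed, and under a constant slope the calculations show no measurable loss. The change counts as prespecified only if made before the study data are unblinded. After that, keep the planned model for the formal tests and report the extended one as supportive.

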4. LIST OF ABBREVIATIONS AND DEFINITIONS OF TERMS

A list of abbreviations and definition of terms is in Table 6.

Table 6:Abbreviations and Definition of Terms	Table 6:	Abbreviations and	l Definition	of Terms
---	----------	-------------------	--------------	----------

Abbreviation or Specialist Term	Full Form/Definition
AE	Adverse event
ALP	Alkaline phosphatase
ALT	Alanine aminotransferase
ANC	Absolute neutrophil count
AST	Aspartate aminotransferase
β-hCG	Beta-human chorionic gonadotropin
BCRP	breast cancer resistance protein
bid	Twice daily
biw	Twice weekly
BPI	Brief Pain Inventory
BPI-SF	Brief Pain Inventory-Short Form
CDC	Centers for Disease Control and Prevention
CGIC	Clinician global impression of change
CGIS	Clinician global impression of severity
CI	Confidence interval
ClinRO	Clinician reported outcome
СО	Crossover
СРК	Creatine phosphokinase
CR	Complete response
CSF1	Colony-stimulating factor 1
CSF1R	Colony-stimulating factor 1 receptor
CTCAE	Common Terminology Criteria for Adverse Events
DLT	Dose-limiting toxicity
DMC	Data monitoring committee
DOR	Duration of response
ECG	Electrocardiogram
eCRF	Electronic case report form
EOT	End-of-Treatment
EQ-5D-5L	5-level EQ-5D

Abbreviation or Specialist Term	Full Form/Definition
EQ-VAS	EuroQol Visual Analogue Scale
FACIT	Functional Assessment of Chronic Illness Therapy
FACT-G	Functional Assessment of Cancer Therapy-General
FDA	U.S. Food and Drug Administration
FSH	Follicle-stimulating hormone
GCP	Good Clinical Practice
G-CSF	Granulocyte colony-stimulating factor
GCT-TS	Giant cell tumor of the tendon sheath
GM-CSF	Granulocyte macrophage-colony-stimulating factor
HIV	Human immunodeficiency virus
IB	Investigator's Brochure
ICF	Informed consent form
ICH	International Conference on Harmonisation
IEC	Independent Ethics Committee
IRB	Institutional Review Board
IRR	Independent radiological review
IRT	Interactive response technology
ITT	Intent-to-Treat
LLN	Lower limit of normal
MedDRA	Medical Dictionary for Regulatory Activities
MMRM	Mixed model for repeated measurements
mRECIST	Modified RECIST
MRI	Magnetic resonance imaging
NASH	Nonalcoholic steatohepatitis
NCI	National Cancer Institute
NRS	Numeric rating scale
OCT2	Organic cation transporter 2
ORR	Objective response rate
PD	Progressive disease
PF	Physical Function
PGIC	Patient global impression of change
PGIS	Patient global impression of severity

Abbreviation or Specialist Term	Full Form/Definition
CCI	
РК	Pharmacokinetic(s)
РР	Per-protocol
PR	Partial response
PRO	Patient-reported outcome
PROMIS	Patient-reported Outcomes Measurement Information System
PROMIS-PF	PROMIS-Physical Function
QoL	Quality of life
QTcF	QT interval corrected by Fridericia's formula
REB	Research Ethics Board
RECIST	Response Evaluation Criteria in Solid Tumors
ROM	Range of motion
RP2D	Recommended Phase 2 dose
SAE	Serious adverse event
SAP	Statistical analysis plan
SD	Stable disease
SOD	Sum of Diameters
SUSAR	Suspected unexpected serious adverse reaction
TDS	Tissue damage score
TEAE	Treatment-emergent adverse event
TGCT	Tenosynovial giant cell tumor
TVS	Tumor volume score
ULN	Upper limit of normal
WHO	World Health Organization
WOCBP	Woman of childbearing potential

